### **3.2 Exclusion Criteria**

Participants not meeting all criteria above in [Section 3.1](#) are ineligible.

### **3.3 Number of Participants to be Enrolled**

NIH policy requires that women and members of minority groups and their subpopulations be included in all NIH-supported biomedical and behavioral research projects involving NIH-defined clinical research unless a clear and compelling rationale and justification establishes to the satisfaction of the funding Institute & Center (IC) Director that inclusion is inappropriate with respect to the health of the participants or the purpose of the research. Exclusion under other circumstances must be designated by the Director, NIH, upon the recommendation of an IC Director based on a compelling rationale and justification. Cost is not an acceptable reason for exclusion except when the study would duplicate data from other sources. Women of childbearing potential should not be routinely excluded from participation in clinical research. Please see <http://grants.nih.gov/grants/funding/phs398/phs398.pdf>.

#### **3.3.1 Proposed sample size**

This study will enroll a minimum of 10 participants per site. If fewer than 10 participants are identified at a site, the AMC will work with site on improvement of potential participant identification. A maximum of 400 participants will be accepted for this registration study. Accrual will be completed once the target trial duration has elapsed.

#### **3.3.2 Accrual rate**

Approximately 2 participants per month per site.

### 3.3.3 Expected Enrollment Demographics

INTERNATIONAL PLANNED ENROLLMENT REPORT (TREATMENT)						
Racial Categories	Ethnic Categories				Total	
	Not Hispanic or Latino		Hispanic or Latino			
	Female	Male	Female	Male		
Indigenous	0	0	14	26	40	
Asian	0	0	0	4	4	
Native Hawaiian or Other Pacific Islander	0	0	0	0	0	
Black or African	0	0	6	10	16	
White	0	0	50	110	160	
More Than One Race	0	0	60	120	180	
Total	0	0	130	270	400	

### 3.4 Participant Enrollment Procedures

Sites must have this protocol approved by their Institutional Review Boards (IRB) and be registered for study participation with the AMC Operations and Data Management Center (ODMC) before they may enroll participants.

After it has been determined that the participant is eligible and an informed consent form has been signed by the participant, the participant must be registered on-line via the AMC Advantage eClinicalSM Internet Data Entry System (Advantage eClinical). Enrollment and data collection will occur via the AMC Internet Data Entry System.

The participating site will ensure a participant meets all eligibility criteria prior to completing the protocol-specific eligibility checklist in Advantage eClinical for enrollment. Participants must be enrolled on-line via Advantage eClinical within 1 week of consent. Once the eligibility checklist is submitted a system-generated confirmation email will be sent to the enroller upon successful completion of the participant enrollment. If the on-line system is inaccessible, the site should notify the AMC ODMC (via email at [[contact]](mailto:[contact]) or via phone at [name]) for further instructions.

#### **4.0 TREATMENT PLAN**

This is a descriptive study. No intervention will be administered as part of this protocol. Please refer to the clinical and laboratory evaluations and statistical sections for a description of the trial procedures.

## **5.0 ADVERSE EVENTS: LIST AND REPORTING REQUIREMENTS**

As this study is non-interventional and focuses on data collection for cancer diagnosis and treatment initiation with limited follow-up, no adverse event data will be collected.

## **6.0 PHARMACEUTICAL INFORMATION**

Not applicable (non-interventional study).

## **7.0 CLINICAL AND LABORATORY EVALUATIONS**

Evaluations required for this protocol are enumerated below and summarized in the Schedule of Events in [Appendix I](#).

### **7.1 Screening**

All presenting HIV+ participants with a histologically confirmed diagnosis of cancer (prior, within 5 years, or current) will be tracked on a screening list and approached to participate in AMC-S008.

To determine the types of cancer cases that present to the clinical sites, it is requested that all participants presenting at these sites have a minimum set of data collected. As this will be performed prior to formal consent, this data collection will be done in a de-identified fashion. Data collected on participants presenting to the clinical site will include the participant's age, sex at birth, and type of cancer. This information will be maintained separately from data on enrolled cases and will not be recorded with any codes or data elements that could be linked to the participant's identity. This data will be compared to the total number of enrolled participants at each site to estimate the proportion of participants who consent to participate in this trial.

### **7.2 Enrollment Data Collection**

Following informed consent, additional, identifiable data will be collected, as outlined below.

7.2.1 Age, date of birth, sex at birth

7.2.2 Whether current HIV care is being received at the enrolling institution, current ART regimen, date of HIV diagnosis, method of HIV diagnosis, current opportunistic infections, current medications.

7.2.3 Current ECOG performance status (see [Appendix II](#))

7.2.4 Estimated life expectancy

7.2.5 Status of cancer diagnosis (one of the following)

- New diagnosis, pre-treatment phase
- New diagnosis, treatment phase
- Prior diagnosis, in remission (within 5 years of initial diagnosis)
- Prior diagnosis, recurrent, pre-treatment phase
- Prior diagnosis, recurrent, treatment phase
- Prior diagnosis, recurrent, no treatment planned

7.2.6 For participants with a new diagnosis (pre-treatment or treatment), the following will be collected:

7.2.6.1 Cancer diagnosis, date of diagnosis, method of diagnosis (cytology, histology), type of pathology performed (H&E, immunohistochemistry, other), data of pathology, staging, staging methods (clinical, radiographic, surgical), date(s) of staging, most recent laboratory values (this would

include complete blood count, renal and liver function, electrolytes, CD4 count, and HIV viral load).

7.2.6.1 Detailed planned or current treatment. This should encompass surgical interventions, radiotherapy, and chemotherapy (agent names), including dates of planned or current therapy, and whether cancer care is being received or will occur at the enrolling institution.

7.2.7 For participants with a prior diagnosis in remission, the following will be collected:

- Cancer diagnosis, date of diagnosis
- Current method of post-treatment surveillance (clinical, laboratory, radiographic), and current schedule of follow-up with this center, current laboratory values (this would include complete blood count, renal and liver function, electrolytes, CD4 count, and HIV viral load).
- Prior method of diagnosis (cytology, histology), pathology performed, date of pathology, staging, staging methods (clinical, radiographic, surgical). Records from a prior diagnosis/treatment should be requested, but if they are unavailable, participant report will be sufficient.
- Prior treatment. This should encompass surgical interventions, radiotherapy, and chemotherapy. Records from a prior diagnosis/treatment should be requested, but if they are unavailable, participant report will be sufficient.

7.2.8 For participants with a prior diagnosis, recurrent (pre-treatment, treatment, or no planned treatment) the following will be collected:

- Initial cancer diagnosis, date of diagnosis
- Prior method of diagnosis (cytology, histology), pathology performed, date of pathology, staging, staging methods (clinical, radiographic, surgical), date(s) of staging. Records from a prior diagnosis/treatment should be requested, but if they are unavailable, participant report will be sufficient.
- Prior treatment. This should encompass surgical interventions, radiotherapy, and chemotherapy. Records from a prior diagnosis/treatment should be requested, but if they are unavailable, participant report will be sufficient.
- Current date of cancer diagnosis, method of diagnosis (clinical, cytology, histology), pathology performed, date of pathology, staging, staging methods (clinical, radiographic, surgical), date(s) of staging, current ECOG Performance Status (PS), current laboratory values (this would include complete blood count, renal and liver function, electrolytes, CD4 count, and HIV viral load).
- IF THERAPY IS PLANNED OR UNDERWAY: Detailed planned or current treatment. This should encompass surgical interventions, radiotherapy, and chemotherapy, dates of planned or current therapy, and whether cancer care is being received or will occur at the enrolling institution.
- IF NO THERAPY IS PLANNED: Reason for no further therapy, e.g., if the decision for no therapy is based on lack of options for treatment, lack of benefit

of further treatment, or participant choice not to pursue further treatment.

### **7.3 Follow-up Evaluations**

For any participants enrolled in AMC-S008, with either planned or current therapy, for both new diagnosis and prior diagnosis, recurrent, a short interval follow-up will be conducted at 4 weeks (+ 6 weeks). Participants can be contacted in person during a planned return visit within this window or can be contacted by telephone if no further clinical appointments occur within this window. If the participant cannot be reached and the information is available in an electronic medical file, this follow up can occur passively via review of medical records.

7.3.1 Is the participant still in follow-up? Last date participant seen in clinic. Current vital status, current ECOG PS.

7.3.2 Current status of treatment plan: planned, no longer planned, ongoing, completed.

7.3.3 For participants in whom treatment is still planned.

- Has the planned therapy changed since enrollment?
- Is the planned start date the same as prior?
- If the planned start date has changed, the reason.

7.3.4 For participants in whom treatment is no longer planned.

- Why the treatment is no longer planned?

7.3.5 For participants in whom treatment is in process.

- Is the current therapy different than the prior planned treatment?
- Start date of current therapy?
- If start date changed, the reason.
- Have there been any delays in treatment thus far, and if so, why?

7.3.6 For participants who have completed therapy.

- Date therapy completed.
- Was therapy completed because planned treatment had been achieved, treatment determined to not be of benefit, change to new therapy based on toxicity or progression, or another factor?

## 8.0 MEASUREMENT OF EFFECT

This is a non-interventional protocol. All data reported on the effect of prior treatment for malignancy will be reported based on existing medical records or the local standard of care.

The following definitions will be employed for case classification and data reporting.

First-line therapy	All therapy performed as part of a treatment plan with a new diagnosis of cancer, including surgery, radiotherapy, and chemotherapy, alone or in combination.
Therapeutic encounter	The period between initiation of a planned therapy and completion of that episode of planned therapy. If the planned therapy changes due to changing clinical circumstances, this is now a new therapeutic encounter (e.g., with progression on first-line therapy R-CHOP, the next treatment is a new therapeutic encounter).
Site-specific frequency of new cases	Total number of participants that present to the site with a first diagnosis of cancer. This encompasses the period from histologically proven cancer to completion of planned first-line therapy or discharge with no anti-cancer treatment planned.
Site-specific frequency of new and existing cases	Total number of participants that present to the site with a diagnosis of cancer within the last 5 years. This includes participants in treatment, surveillance, or best supportive care.
New diagnosis	Status that includes the period from histologically proven cancer to completion of all planned first-line therapy. A second malignancy will be captured as a new diagnosis. Examples include a transformed lymphoma in the setting of the low-grade lymphoma or development of vulvar cancer in the setting of a history of treated cervical cancer.
Prior diagnosis, in remission	Status that includes the period from completion of first-line therapy until evidence of disease progression. This could encompass participants with no evidence of disease or stable disease that is not progressing.
Prior diagnosis, recurrent	Status that includes the period following evidence of progression of the previously diagnosed cancer in a participant who has completed a prior therapy. This does not encompass new second malignancies.
Pre-treatment phase	The period in which a participant has a histologically diagnosed cancer, with cancer-specific treatment planned but not yet initiated.
Treatment phase	The period in which the participant has started therapy for cancer. This can include surgery, radiation, and/or chemotherapy. This period completes when all planned therapy has been completed within a therapeutic encounter.
No treatment planned	The point at which no further active cancer treatments are

	planned. Initiation of best supportive care or palliative care.
--	---

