#### **3.1 Eligibility Criteria**

3.1.1 HIV positive. Documentation of HIV-1 infection by means of any one of the following:

- Documentation of receipt of ART by a licensed health care provider (Documentation may be a record of an ART prescription in the participant's medical record, a written prescription in the name of the participant for ART, or pill bottles for ART with a label showing the participant's name);
- HIV-1 RNA detection by a licensed HIV-1 RNA assay demonstrating >1000 RNA copies/mL, and supported by a licensed screening antibody and/or HIV antibody/antigen combination assay;
- Any licensed HIV screening antibody and/or HIV antibody/antigen combination assay confirmed by a second licensed HIV assay, such as a HIV-1 Western blot confirmation or HIV rapid multispot antibody differentiation assay.

Note: The term "licensed" refers to a kit that has been certified or licensed by an oversight body within the participating country and validated internally.

WHO (World Health Organization) and CDC (Centers for Disease Control and Prevention) guidelines mandate that confirmation of the initial test result must use a test that is different from the one used for the initial assessment. A reactive initial rapid test should be confirmed by either another type of rapid assay or an E/CIA that is based on a different antigen preparation and/or different test principle (e.g., indirect versus competitive), or a Western blot or a plasma HIV-1 RNA viral load.

3.1.2 Must have a current or prior (within the last 5 years) diagnosis of cancer – but there is no restriction of the number or type of prior treatments. Participants will qualify under one of three categories:

- New diagnosis – no prior treatment for current malignancy. May be prior to, or currently receiving the first line of therapy.
- Prior diagnosis (within 5 years), in remission – Not currently on cancer treatment other than cART. Prior treatment for malignancy can include surgery, radiation, or chemotherapy (or cART initiation in KS). No restriction on number of prior lines of therapy.
- Prior diagnosis, recurrent – Considering or currently receiving treatment that is not first line. No restriction on the number of prior lines of therapy

\_\_\_\_\_ 3.1.3 Age > 18 years. Date of birth and age should be determined based on best possible information or documentation available.

\_\_\_\_\_ 3.1.4 Ability to understand and the willingness to provide informed consent document.

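### Section 8 classes remission after second or later therapy as recurrent, whereas eligibility criterion 3.1.2 classes it as in remission; two smaller ambiguities belong in the same edit

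*Combined protocol and SAP*

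**What the plan says.** The primary objective (1.1) takes its case categories from 3.1.2. Section 8 supplies its own definitions of the same categories and says of them: "The following definitions will be employed for case classification and data reporting". Neither place says which prevails.

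- **Remission.** In 3.1.2 the participant is "Not currently on cancer treatment other than cART", with "No restriction on number of prior lines of therapy". In Section 8 it is "Status that includes the period from completion of first-line therapy until evidence of disease progression".
- **Recurrent.** In 3.1.2 the participant is "Considering or currently receiving treatment that is not first line". In Section 8 the status begins at progression, "in a participant who has completed a prior therapy", and no end is given.
- **New diagnosis.** In Section 8 this lasts until all planned first-line therapy has been completed.
- **Five-year window.** Entry under 3.1.2 reads "Must have a current or prior (within the last 5 years) diagnosis of cancer", and the recurrent category there carries no time limit of its own. The Section 8 count of new and existing cases is "Total number of participants that present to the site with a diagnosis of cancer within the last 5 years".

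Status decides which enrollment data are collected: 7.2.6 for new diagnoses, 7.2.7 for remission, 7.2.8 for recurrence. Section 9.1 estimates the number of new and existing cases by site and cancer type. It specifies no analysis by status.

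**The concern.** A participant who relapsed, completed second-line therapy and is now under surveillance gets a different status depending on which section the site follows. Under Section 8 the case is recurrent. Of the three recurrent options in 7.2.5, the nearest is the one with no treatment planned, which Section 8 links to supportive or palliative care. A successfully treated surveillance case would then be recorded alongside palliative cases. It would be asked why no therapy is planned, and the current surveillance method and follow-up schedule required by 7.2.7 would not be collected.

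The study exists to describe what presents at each site. If sites follow different sections, their remission and recurrent figures are not comparable.

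Two neighbouring definitions leave a similar choice open. One is whether first-line therapy abandoned because of progression has been completed, which affects the split between new and recurrent cases. The other is which diagnosis date the 5-year count uses when a cancer recurs.

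**Working it through.** The plan states no figure on this point, so there is none to reproduce. The check applies each definition literally to three kinds of case.

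| Case | 3.1.2 | Section 8 |
|---|---|---|
| Remission after second or later therapy | In remission | Recurrent: remission ended at the first progression, and recurrent has no end |
| Progression during first-line therapy, next line considered or given | Recurrent | Read literally, still new or without a clear status; recurrent if stopping for progression counts as completion |
| Current recurrence, first diagnosed more than 5 years ago | Recurrent | Recurrent; counted if the recurrence date is used, not counted if the initial date is used |

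**Row 1** is a direct contradiction.

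**Row 2** can be reconciled. Item 7.3.6 lists a switch of therapy for progression among the reasons therapy was completed, and Section 8 treats the next treatment after first-line progression as a new therapeutic encounter. Both point to *recurrent*. However, 7.3.6 is a follow-up question, and Section 8 does not define completion.

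**Row 3** is an unstated anchor date. Table 2-A and 7.2.5 anchor the window for remission on the initial diagnosis. Item 7.2.8 records a separate current diagnosis date for recurrences.

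**Effect on the counts, for scale only.** Inputs: about 2 participants per month per site (3.3.2) and 21 months (2.2), so 2 × 21 = 42 per site. The exact 95% Poisson interval for a count x runs from χ²(0.025; 2x)/2 to χ²(0.975; 2x + 2)/2. For x = 42 it is 30.3 to 56.8.

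- *Row 1.* Assume an equal split of 14 new, 14 in remission and 14 recurrent. Moving 2, 4 or 8 cases from remission to recurrent gives 12 and 16, 10 and 18, or 6 and 22. The total stays 42 each time.
- *Row 2.* Cases move between new and recurrent. The combined total is again unchanged, but Section 8's separate frequency of new cases can change.
- *Row 3.* Assume that 5%, 10% or 20% of the 42 are late recurrences and that the initial date is used:
  - 5% × 42 = 2.1, so about 2 are dropped, leaving 40 (28.6 to 54.5).
  - 10% × 42 = 4.2, so about 4 are dropped, leaving 38 (26.9 to 52.2).
  - 20% × 42 = 8.4, so about 8 are dropped, leaving 34 (23.5 to 47.5).

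**Effect on follow-up.** Section 7.3 follows new and recurrent cases that have planned or current therapy, and Appendix I exempts those with no further treatment planned. A second remission has none planned, so it is not followed under either label. Progression on first-line therapy with further therapy is followed under either label. Follow-up of a late recurrence depends on therapy, not on the 5-year count.

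**The case against.** The best defence is that sites would probably get this right. Section 8 says each status includes a period, which is not strictly exclusive wording. None of the recurrent options in 7.2.5 suits a person in second remission, so *in remission* is the natural entry. The 7.2.7 and 7.2.8 data sets also overlap on initial diagnosis, prior staging, prior treatment and laboratory values. This limits the practical damage but does not remove the contradiction: Section 8 is the declared rule for classification, and followed as written it gives the other answer and omits the surveillance items.

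The rest of the defence largely stands, and it rules out several stronger readings that a reader might infer:

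- *That progression on first-line therapy has no category.* Item 7.3.6 and the therapeutic-encounter definition allow it to be recurrent, in agreement with 3.1.2.
- *That late recurrences are excluded from the count.* The count definition does not say initial diagnosis, 7.2.8 gives a recurrence its own diagnosis date, and the primary objective expressly includes recurrences. They drop out only on a reading that the text does not require.
- *That the remission contradiction distorts the primary total.* That total combines new and existing cases, and Section 8 includes treatment, surveillance and supportive care in it.
- *That people are wrongly placed in or out of follow-up.* Follow-up turns on therapy, and the disputed label does not change it.

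**Conclusion.** One contradiction is confirmed: remission after second or later therapy is *in remission* under 3.1.2 and *recurrent* under Section 8. It affects the status breakdown and the choice between the 7.2.7 and 7.2.8 data sets. It leaves the combined primary count and the 7.3 follow-up unchanged.

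Two ambiguities should be settled with it. Whether therapy stopped for progression counts as completed affects the new-versus-recurrent split and the frequency of new cases. The anchor date for recurrences is the only one of the three points that could alter the primary total.

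The documents give no mix of statuses and no share of late recurrences. The equal split and the 5% to 20% range are assumptions for illustration, and the 42 per site is only the planned enrollment rate multiplied by the period. The point is worth correcting because a rule declared to govern classification gives the wrong status for an identifiable group and the repair is simple.

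**What to change.** Reconcile Section 8 with 3.1.2 in one edit:

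1. Define *in remission* as running from completion of the most recent planned therapy until progression.
2. Define *recurrent* as running from progression until the subsequent planned therapy is completed without further progression, or for as long as no treatment is planned for progressive disease. The end point matters: if only the remission definition were changed, a second remission would meet both definitions.
3. State that therapy ended because of progression counts as completed. This closes *new diagnosis* and opens *recurrent* for progression on first-line therapy.
4. In the count of new and existing cases, state that a current recurrence enters the 5-year window by its current diagnosis date.

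The CRF instructions for the 7.2.5 status item should carry the same wording. No new data item is needed, because 7.2.8 already collects both the initial and the current diagnosis date. The cost is definition wording and CRF instructions, processed as a written amendment under Section 11.2.
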